D1734-P

Effect of Heat Exposure on Cognition in Persons With Higher Cord Lesions

September 9, 2014

The increased variability in Tcore of persons with SCI has been demonstrated in a previous study. Nine subjects with tetraplegia and 8 matched controls ingested a capsule which transmitted information on temperature to a portable receiver (manuscript in preparation). Subjects were sent home to perform their usual routines (i.e., their activities and environments were not controlled). Tcore was measured 3 times when the capsule was in the small intestine. The variance in the mean of these 3 measurements was more than 200% greater in those with tetraplegia than in controls (0.71 ± 0.06 versus 0.31 ± 0.04 ; respectively, $p < 0.01$).

Research Design and Methods

Research Design: Methods: A prospective, two-group comparative study will be performed to determine the effects of warm thermal challenge on Tcore, cognitive performance, distal skin temperature (Tsk), sweat rate (QS), and subjective rating of thermal sensitivity (TS) in individuals with SCI (tetraplegia and high paraplegia) and in a matched AB control group in the seated position.

Subjects: Twenty subjects with higher cord lesions (C3-T4; AIS A & B) and 20 non-SCI controls, matched for age (± 5 years) and gender will be recruited for study.

Subject Recruitment: Patients referred by their physician following routine physical examinations will be approached for possible study enrollment. Physicians will be informed of the inclusion and exclusion criteria and will be able to assure us that the patient is an appropriate study participant and that he/she is willing to speak with the study coordinators.

1. Veterans with SCI responding to IRB approved articles in lay publications and advertisements.
2. Veterans with an ongoing relationship with our center (Metabolic, Pulmonary, or GI SCI clinics).

- a. **Inclusion Criteria:** (1) Between 18 and 65 years of age; (2) Duration of injury ≥ 1 year; (2) Level of SCI C3-T4, AIS A & B; (3) Tcore at BL $< 37.0^{\circ}\text{C}$; (4) Euhydration; and (5) Gender and age-matched (± 5 years) AB controls (between 18-65 years of age).
- b. **Exclusion Criteria:** (1) Known heart, kidney, peripheral vascular or cerebral vascular disease; (2) High blood pressure; (3) History of TBI or diagnosed cognitive impairment; (4) Untreated thyroid disease; (5) Diabetes mellitus; (6) Acute illness or infection; (7) Dehydration; (8) Smoking; (9) Pregnancy; and (10) Broken, inflamed, or otherwise fragile skin.

[figure not shown]
Preparation for Study Visits: Subjects [will be instructed to avoid caffeine and alcohol, maintain normal salt and water intake, and avoid strenuous exercise for 24 hours prior to study and] will enter the laboratory between 8:00-10:00 AM on each study visit. Subjects will wear minimal clothing during the study to maximize skin exposure to the warm temperature. Each subject will be asked to eat a light, standard meal (plain bagel or 2 pieces of toast) 2 hours prior to their visit. Subjects will be asked to empty their bladders prior to each study visit and again upon arrival, if needed.

Warm Ambient Exposure: Instrumentation: Subjects with SCI will be asked to remain in their wheelchairs and AB controls will be placed in a manual wheelchair, where they will [remain seated and relatively still] for the duration of the study visit. A rectal probe will be placed 10 cm beyond the anal sphincter for Tcore collection, and skin thermocouples will be secured at 15 sites above and below the level of lesion (e.g., bilateral toes, feet, thighs, upper and lower chest, triceps, hands, fingers, and forehead) for collection of skin temperature. Sweat collection capsules will be placed on the left lateral anterior shoulder, volar aspect of the distal forearm, proximal anterior thigh and the mid-lateral calf (dermatomes C5, T1, L3, L5) for measurement of sweat rate by QSweat methodology (QS). Laser Doppler flowmetry will be used to measure changes in microvascular perfusion (MVP) by placing a Doppler probe on the dorsal surface of both hands and feet to confirm peripheral vasodilatation. An automated blood pressure cuff will be placed above the left elbow to measure brachial BP.

Procedures: The following measurements will be obtained during BL, Thermal Challenge & Recovery periods. *Tcore*: will be monitored by a TX-2 Rectal probe and Iso-Thermex Multichannel Thermometer (Columbus Instruments, Columbus, OH). The probe will be placed 10 cm beyond the anal sphincter. *Skin Temperature (Tsk)*: will be monitored using TX-4 Skin Surface probes and Iso-Thermex Multichannel Thermometer (Columbus Instruments, Columbus, OH). Skin thermocouples will be taped to 15 sites above and below the SCI level.

Sweat Rate (QS): will be measured using Q-Sweat (Quantitative Sweat Measurement System, WR Medical Electronics Co., Minnesota) and 4 sweat collection capsules. *Microvascular Perfusion (MVP)*: will be measured using laser probes on the skin of the dorsum of both hands and feet and a Periflux System 5000 Laser Doppler (Perimed, Stockholm, Sweden). *Thermal Sensitivity (TS)*: will be measured by a 9-point thermal sensation scale. (Appendix 3)

Cognitive Performance Battery: The cognitive battery will be administered once at BL and once after Tcore has increased 0.5°C after thermal challenge (in tetraplegics) or after 100 minutes of Heat (in controls). [Testing conditions will be identical, quiet and distraction-free.] *Wechsler Adult Intelligence Scale-Fourth Edition (WAIS-IV)*: Subjects will be asked to repeat 2-9 numbers forward, backward or in ascending order to assess attention, processing speed, and working memory. ⁷⁰⁻⁷² *Memory section (Delayed Recall) of the Montreal Cognitive Assessment (MoCA)*: Subjects will be asked to repeat 5 simple words immediately and then recall them after a 5 minute delay to assess working memory. ⁶⁹ *Stroop Color and Word*: Subjects will be asked to read words of colors, colors of fonts to assess attention and processing speed; color of fonts of words which describe conflicting colors to assess response inhibition (executive functioning). ⁷³ [Subjects will practice each of the assessments for approximately 10 seconds prior to the actual test to insure understanding of the instructions.]

Hemodynamic Measurement Procedures: *Brachial Blood Pressure*: will be measured at the right brachial artery using the Carescape Dinamap V100 Automated BP Monitor (Carescape, Milwaukee, WI). BP will be obtained at 10 minute-intervals throughout BL, Thermal Challenge, and Recovery periods.

Sample Size and Statistical approach: Based on power analysis from our preliminary data in 8 subjects with tetraplegia, we determined that a sample size of 20 subjects per group would be needed to achieve a power of 97.34% for a double-sided 2 sample analysis at an alpha of 0.05. If 5 subjects per group are lost to attrition, the power would be 91.66%. The primary aims that 80% of the subjects with SCI will demonstrate an increase of 0.5°C in Tcore and an increase of at least one T-score in Stroop Interference (executive function) will be analyzed using one-sample chi square tests. Secondary physiological and cognitive variables will be compared between groups using multivariate analyses (MANOVA). Significant group main effects from the MANOVA model will be further analyzed using unpaired t-tests. Percent changes from BL will be calculated for all variables and analyzed for significance against zero (i.e., no change) using one-sample tests.

Table 1: Schedule of Assessments and Procedures

Measures	Acclimation	BL	Heat	Recovery
Run Time (min)	30	15	120†	30
Cumulative Time (min)	30	45	165	195
TCore		††	††	††
Skin Temperatures		††	††	††
Brachial BP		2x	12x	3x
Sweat rate (QS)			1x	3x
Thermosensitivity Scale	1x	2x	12x	2x
Microvascular Perfusion		2x	3x	
Cognitive Battery		1X	1X	

† Heat will continue until Tcore increases 0.5°C, or until 120 minutes. †† Tcore and skin temperature measurements will be monitored and collected continuously throughout the study.

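### The stated power (97.34%, or 91.66% after attrition) is for a two-sample analysis, but both primary aims use one-sample chi-square tests in which the role of 80% is not stated

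*Combined protocol and SAP*

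**What the plan says.** All of the statistical text is one paragraph, headed Sample Size and Statistical approach.

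- **Power.** From preliminary data in 8 subjects with tetraplegia, it concludes that "a sample size of 20 subjects per group would be needed to achieve a power of 97.34% for a double-sided 2 sample analysis", with alpha 0.05. It adds: "If 5 subjects per group are lost to attrition, the power would be 91.66" (percent). The variable, effect size, standard deviation and specific test are not given.
- **Primary analysis.** The next sentence begins "The primary aims that 80% of the subjects with SCI will demonstrate" and lists two criteria: a Tcore rise of 0.5°C, and a gain of one T-score or more on Stroop Interference. These "will be analyzed using one-sample chi square tests". No proportion is labelled as null or alternative, and no power is given for these tests.
- **Between-group analysis.** Comparison of the two groups appears only for secondary variables, by MANOVA followed by unpaired t-tests.

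Under Research Design and Methods the study is described as two-group ("A prospective, two-group comparative study will be performed to determine the effects of warm thermal challenge"). The SCI group is "Twenty subjects with higher cord lesions", with 20 matched controls.

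**The concern.** The power statement and the primary analysis concern different comparisons. A two-sample analysis uses 40 subjects and a difference between groups. The primary tests use only the 20 SCI subjects, or 15 after the stated attrition, and compare one proportion with a reference value. A reader who takes 97.34% as the chance of meeting a primary aim takes it from the wrong test.

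The role of 80% matters more. A one-sample chi-square test measures departure from a reference proportion, and 80% is the only proportion in the text. If it is the reference, a finding in line with the aim (16 of 20) gives a test statistic of zero. If it is the rate the sponsor expects, the reference has still to be named. Either way, the paragraph does not say what result would show that a primary aim was met.

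**Working it through.** **Inputs from the protocol:** 20 SCI subjects; 20 − 5 = 15 after attrition; two-sided alpha 0.05 (stated for the two-sample analysis, assumed here for the primary tests); 80%; stated powers 97.34% and 91.66%. **Assumed, because the text gives none:** null proportions of 30% to 60% when 80% is the expected rate; true rates of 60% and 90% when 80% is the null.

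**1. The plan's own figures.** 97.34% cannot be reproduced from the text, since no effect size is given. Consistency can be checked by solving for the standardized difference d that gives 97.34% at n = 20 per group, then recomputing at 15. For a two-sided two-sample t-test, power = P(T > t₀.₉₇₅), where T is noncentral t with 2n − 2 degrees of freedom and noncentrality d√(n/2).

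- n = 20: d = 1.264 gives 97.34%.
- n = 15: the same d gives 91.62% (stated 91.66%).

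Other tests fitted the same way give similar values at n = 15: normal approximation 92.1%, two proportions 91.3%, one-sample t 91.1%. The two stated powers agree with each other, but they do not reveal which test or variable they came from.

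**2. If 80% is the null.** The test rejects when (X − np₀)² / [np₀(1 − p₀)] > 3.841. With a continuity correction, |X − np₀| is first reduced by 0.5.

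- n = 20: np₀ = 16, variance 3.2. X = 20 gives 16/3.2 = 5.00 and rejects. X = 19 gives 9/3.2 = 2.81 and does not. With correction, X = 20 gives 3.5²/3.2 = 3.83, which does not reject. Exact binomial for X = 20: 0.8²⁰ = 0.0115 plus a lower tail of 0.0100 gives p = 0.0215, which rejects.
- n = 15: np₀ = 12, variance 2.4. X = 15 gives 9/2.4 = 3.75, or 2.5²/2.4 = 2.60 corrected. Exact: 0.8¹⁵ = 0.0352 plus 0.0181 gives p = 0.053. No variant rejects upward.
- With a true rate of 90%, the chance of upward rejection at n = 20 (uncorrected or exact) is 0.9²⁰ = 12.2%. At n = 15 it is zero.
- Non-rejection covers 13-19 of 20 (uncorrected or exact), 12-20 of 20 (corrected) and 9-15 of 15 (all variants). A true rate of 60% therefore goes unrejected 41.6% or 59.6% of the time at n = 20, and 61.0% at n = 15.

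**3. If 80% is the expected rate.** Find the smallest X that rejects upward, then sum exact binomial probabilities at p = 0.8. Example, null 50%: at n = 20, X = 15 gives 5²/5 = 5.00 and X = 14 gives 4²/5 = 3.20, so the limit is 15 and P(X ≥ 15) = 80.4%. At n = 15, X = 12 gives 4.5²/3.75 = 5.40 and X = 11 gives 3.5²/3.75 = 3.27, so the limit is 12 and P(X ≥ 12) = 64.8%.

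| Assumed null | Limit, n = 20 | Power, n = 20 | Limit, n = 15 | Power, n = 15 |
|---|---|---|---|---|
| 30% | 11 | 99.7% | 8-9 | 98.2-99.6% |
| 40% | 13 | 96.8% | 10-11 | 83.6-93.9% |
| 50% | 15 | 80.4% | 12 | 64.8% |
| 60% | 17 | 41.1% | 13-14 | 16.7-39.8% |

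Ranges span the uncorrected, continuity-corrected and exact tests. At n = 20 all three agree for every null shown.

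**The case against.** The best reply is that 80% is the stated reference value: it is the only proportion given, it sits in the sentence that names the test, and a chi-square against 80/20 can be run as written. This stands to the extent that the null is not simply absent. The role of 80% is ambiguous. The reply does not rescue the analysis, because step 2 shows that this test cannot show the aim.

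The available text also reads like an extract. It cites preliminary data without tabulating them, so the variable behind 97.34% may be recorded elsewhere. Statements about what is absent are therefore limited to the available text. The mismatch is not affected, because it lies between adjacent sentences. The nulls in step 3 are assumptions and show only sensitivity. The choice among test variants is a minor detail.

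A reader might infer more than the documents support:

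- *That 97.34% or 91.66% is miscalculated.* The two are mutually consistent.
- *That the study is underpowered.* Without a null this cannot be said; a null of 30% would give more power than stated.
- *That the sponsor means to choose the null after seeing results.* Nothing suggests it.
- *That fewer subjects make the aim easier to pass if 80% is the null.* The text does not say that non-rejection counts as success, and the direction is not general. With a continuity correction, a true 70% goes unrejected 88.7% of the time at n = 20 and 86.9% at n = 15.
- *That the figures belong to the secondary MANOVA, or that a two-group comparison was meant to be primary.* The design would allow either, but the text states neither.

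**Conclusion.** Wrong as written: the stated power does not belong to the primary test. This follows from the wording alone and needs no assumption.

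The role of 80% must also be settled, since neither reading leaves a usable primary test. As the null, 80% can be rejected upward only by 20 of 20, and never with 15 subjects; non-rejection does not establish that 80% respond. As the expected rate, it leaves the null missing, and power runs from 96.8% to 41.1% at n = 20 as the assumed null moves from 40% to 60%. The stated 97.34% is not reached at a null of 40% or above.

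The power figures assume a two-sided 0.05 test of each criterion separately. The plural aims and tests favour that reading, but the text does not say whether 80% applies to each criterion or to both jointly.

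**What to change.** Before data are seen, rewrite the paragraph to:

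1. State that 80% is the expected (alternative) proportion and give a justified null below it for each primary aim, or otherwise restate the hypothesis so that the test can support the aim.
2. Say whether 80% applies to each criterion separately or to both jointly.
3. Replace the power statement with the power of that one-sample test at 20 and 15 SCI subjects, naming the variant used.
4. Attribute 97.34% and 91.66% to their actual variable, effect size and test, or remove them.

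Possible wording: *For each primary aim, the null proportion is [p0], justified by [source], and the expected proportion is 80%. Test: one-sample [variant], two-sided alpha 0.05. Power: [x]% with 20 SCI subjects and [y]% with 15.* For illustration only, 50% against 80% gives 80.4% and 64.8%. The sponsor must choose and justify the null.

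The cost is one paragraph and no additional subjects. The stated power will probably be lower and should be accepted openly. If 80% was meant as the null, the hypothesis itself changes. If the sponsor intended a two-group primary comparison, naming it would change the primary analysis and should be recorded as such.

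### The primary core-temperature aim is tested in SCI subjects alone, so it cannot by itself support a statement about an effect of the cord lesion, although matched controls are measured and the study is powered as a two-sample comparison

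*Combined protocol and SAP*

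**What the plan says.** All references are to the combined protocol and SAP.

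- **Primary aim and test** (Sample Size and Statistical approach). The Tcore aim is that "80% of the subjects with SCI will demonstrate an increase of 0.5°C in Tcore". Together with the Stroop aim, it "will be analyzed using one-sample chi square tests". The null proportion is not given.
- **Between-group testing** (same section). "Secondary physiological and cognitive variables will be compared between groups using multivariate analyses (MANOVA"), with unpaired t-tests to follow. The variables in the MANOVA are not listed.
- **Other tests** (same section). "Percent changes from BL will be calculated for all variables and analyzed for significance against zero (i.e., no change) using one-sample tests". These are also single-group tests.
- **Power** (same section). The plan puts power at 97.34% with 20 subjects in each group, and says that this is "for a double-sided 2 sample analysis at an alpha of 0.05". On dropout it adds: "If 5 subjects per group are lost to attrition, the power would be 91.66"%. No effect size, standard deviation or response rate is stated.
- **Design** (Research Design and Methods). "A prospective, two-group comparative study will be performed to determine the effects of warm thermal challenge on Tcore", followed by the other outcomes. Twenty SCI subjects and 20 controls matched on age and gender are to be recruited.
- **Control data** (Thermal Challenge; Table 1 footnotes). The Heat period runs to a 0.5°C rise or 120 minutes, with no restriction to one group, and Tcore is recorded continuously.

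**The concern.** The design and the power statement are comparative, but the primary Tcore decision is not. Its only input is the number of SCI subjects who reach +0.5°C. It therefore cannot separate two explanations of a high count: that a higher cord lesion makes the rise more likely, or that 35°C for up to 120 minutes produces it in most seated people. The controls are in the study to separate these, and they are half the sample, yet their Tcore plays no part in the primary result.

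At stake is what may be concluded. A result about SCI subjects only is legitimate. If the report goes further and attributes the rise to the lesion, the primary test gives no support for that step.

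**Working it through.** **1. The plan's own power figure.** With no effect size stated, 97.34% cannot be reproduced from inputs, but the two power figures can be checked against each other. For a two-sided two-sample t-test at 0.05, the noncentrality is d·√(n/2) on 2n − 2 degrees of freedom. Setting power to 97.34% at n = 20 per group gives d = 1.264. The same d at n = 15 per group gives 91.62%, against 91.66% stated. The two figures agree with each other and fit a two-sample test. They are not figures for a one-sample chi-square.

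**2. Same primary result, different control outcomes.** Take 16 of 20 SCI responders, exactly 80%. The one-sample chi-square is (x − n·p0)² / (n·p0·(1 − p0)).

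- Against p0 = 0.50: (16 − 10)²/5 = 7.2, p = 0.007.
- Against p0 = 0.80: (16 − 16)²/3.2 = 0, p = 1.00.

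Neither value changes with the controls. Fisher's exact test between groups does:

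| Controls reaching +0.5°C | One-sample result in SCI | Fisher p, SCI vs control |
|---|---|---|
| 2/20 | unchanged | 0.00002 |
| 4/20 | unchanged | 0.0004 |
| 10/20 | unchanged | 0.096 |
| 16/20 | unchanged | 1.00 |

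**3. How often the aim is met when there is no lesion effect.** Let both groups share a true rate p, with 20 SCI subjects. Both p and the null are assumptions, so three readings of the aim are shown:

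- A: significantly above an assumed 50% null. 15/20 gives 25/5 = 5.0, which exceeds 3.84; 14/20 gives 16/5 = 3.2, which does not. So 15 or more are needed.
- B: at least 80% observed, so 16 or more.
- C: significantly above an 80% null. 20/20 gives 16/3.2 = 5.0; 19/20 gives 9/3.2 = 2.81 (p = 0.094). So all 20 are needed.

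Upper binomial tail probabilities:

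| Shared rate p | A: ≥15 | B: ≥16 | C: 20 |
|---|---|---|---|
| 0.3 or less | about 0% | about 0% | about 0% |
| 0.7 | 42% | 24% | 0.1% |
| 0.8 | 80% | 63% | 1.2% |
| 0.9 | 99% | 96% | 12% |

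A two-sided Fisher comparison of the groups would be significant 2.3% of the time at a shared 80% and 1.2% at a shared 90%.

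**4. Power of a between-group comparison.** Two-sided Fisher's exact test at 0.05, full enumeration, SCI rate 80% (the plan's target), control rate assumed:

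| Control rate | 20 per group | 15 per group |
|---|---|---|
| 20% | 96% | 87% |
| 30% | 85% | 68% |
| 40% | 65% | 45% |
| Power falls below 80% at | about 33% | about 25% |

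**The case against.** **The aim is about SCI subjects, and a one-sample test answers it.** This stands. No section says that a positive Tcore result will be taken as evidence of a lesion effect. Because the 0.5°C rise also triggers the second cognitive battery in subjects with tetraplegia, the aim can be read as a check that the challenge reached its target. A lesion-effect claim is something a reader might infer from the two-group design; the plan does not make it. What remains is the mismatch between a single-group primary test and a design and power statement that are comparative.

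**The MANOVA may cover Tcore.** It may: Tcore is first in the list of outcomes, and no MANOVA variable is named, so none is excluded. But the MANOVA is labelled secondary and does not decide the primary aim.

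**Controls are unlikely to warm.** The plan tests controls after 100 minutes of Heat and not at +0.5°C, which suggests that the sponsor expects few to get there. If so, the aim would rarely be met without a lesion effect. This limits the practical risk. It does not remove the gap, because the expected control rate is not stated and the observed one is not used.

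**The large percentages rest on a chosen null.** This also stands. A reader might infer from reading A that the aim is very likely to be met without any lesion effect. The documents do not support that: the 50% null is an assumption, the only proportion the plan names is 80%, and against 80% the figure at a shared rate of 80% is 1.2%. The large figures also need at least 70% of controls to warm.

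**Conclusion.** The point holds in limited form. As written, the primary Tcore result can support a statement about SCI subjects under this heat exposure, but not a statement about an effect of the cord lesion. That follows from the structure of the test and holds under any null proportion.

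The size of the risk is not determined by the documents. At a shared true rate of 80% it runs from 1.2% to 80% depending on how the aim is read, and at 30% or less it is negligible. These figures assume 20 SCI subjects, independent responses and an uncorrected chi-square. The case for change rests on the unused comparison, not on the top of that range. It is a cheap improvement that lets the trial answer the comparative question it sets itself.

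**What to change.** In the statistical section:

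1. Keep the SCI proportion reaching +0.5°C as an estimate with an exact 95% confidence interval.
2. Pre-specify one comparison of SCI subjects with controls in the proportion reaching +0.5°C within the 120-minute Heat period: two-sided Fisher's exact test, with a 95% confidence interval for the difference.
3. State that any claim of an SCI effect on Tcore requires this comparison, and that otherwise the primary claim is limited to SCI subjects.
4. State the power for this contrast and the control rate it assumes.

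**Cost.** A few sentences and a restated power calculation. No new subjects, visits or measurements are needed, because control Tcore is already recorded continuously. The downside is power if controls warm more often than expected. With SCI at 80%, power drops below 80% once the control rate passes about 33% with the full 20 per group, or about 25% in the plan's own attrition case of 15 per group. The assumed control rate should therefore be justified when the power is restated.

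### Controls are matched on age and gender, but the secondary group comparisons ignore the matching and can lose precision; the unpaired t-test variant is also not named

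*Combined protocol and SAP*

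**What the plan says.** The design is a comparison of two non-randomised groups: "A prospective, two-group comparative study will be performed". The Subjects paragraph specifies "20 non-SCI controls, matched for age (± 5 years) and gender will be recruited for study", and the inclusion criteria allow ages 18 to 65. It does not say whether each control is tied to one subject with SCI (pair matching) or the groups are balanced overall (frequency matching).

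The section Sample Size and Statistical approach sets out the analysis:

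- The primary aims concern the SCI group alone and "will be analyzed using one-sample chi square tests".
- For the rest, "Secondary physiological and cognitive variables will be compared between groups using multivariate analyses (MANOVA").
- After that, "Significant group main effects from the MANOVA model will be further analyzed using unpaired t-tests".

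The section mentions no pair effect, paired test, or age or gender covariate. It also does not say whether the unpaired t-test is the pooled-variance or the Welch form.

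The only between-group figures on spread are in the opening background paragraph, for Tcore in 9 people with tetraplegia and 8 controls: "0.71 ± 0.06 versus 0.31 ± 0.04". Of the conditions it says: "Subjects were sent home to perform their usual routines (i.e., their activities and environments were not controlled").

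**The concern.** Matching restricts whom the sponsor can recruit as a control. It pays back in precision only if the analysis uses the pairs or the matching factors. When age and gender affect the outcome, matched subjects resemble each other. The unpaired standard error still counts that shared variation as noise, so intervals are too wide and the test rejects too rarely.

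The affected comparisons are secondary. They are nevertheless the plan's only stated SCI-versus-control inference, because the primary tests use the SCI group alone.

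A smaller point goes with this. The background suggests that Tcore varies more in tetraplegia. If the t-test is run in pooled form and the group sizes become unequal, its standard error can be off. The plan does not rule that out.

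**Working it through.** **1. The plan's own power figures.** The plan states 97.34% power with 20 per group and 91.66% with 15 per group (two-sided, two-sample, alpha 0.05). It gives no effect size or SD, so 97.34% cannot be rebuilt from its inputs. The two figures can be checked against each other. For an unpaired t-test the noncentrality is d·√(n/2) on 2n − 2 degrees of freedom. Solving for 97.34% at n = 20 gives d = 1.264 (noncentrality 1.264 × √10 = 4.00). At n = 15 the same d gives 91.62%, close to the stated 91.66%. The plan is therefore powered as if unpaired, at d of about 1.26 for an unnamed variable.

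**2. Effect of ignoring the pairs.** Let r be the within-pair correlation, with equal SD σ and n = 20 pairs.

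- Unpaired SE = σ√(2/n).
- Correct SE = σ√(2(1 − r)/n).
- Ratio = 1/√(1 − r).

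The values of r and d = 0.8 are assumptions; d = 1.264 comes from step 1. Paired power is from the noncentral t distribution. Unpaired size and power are from simulation (100,000 or more null trials).

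| r | SE ratio | True size, unpaired | Power at d = 0.8, unpaired v paired | Power at d = 1.264, unpaired v paired |
|---|---|---|---|---|
| 0 | 1.00 | 5.0% | 69% v 67% | 97.3% v 96.6% |
| 0.1 | 1.05 | 3.9% | 70% v 72% | 97.9% v 97.9% |
| 0.3 | 1.20 | 2.1% | 73% v 82% | 98.9% v 99.5% |
| 0.5 | 1.41 | 0.7–0.8% | 76% v 92% | 99.6% v 99.96% |

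If matching on age and gender were exact, r would be roughly the share of outcome variance that those two factors explain. A value of 0.5 therefore needs them to explain about half of it, so the lower rows are the safer guide.

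**3. Pooled or Welch.** With equal n, both variance estimates reduce to (s₁² + s₂²)/n, so the standard errors are identical at 20/20 and 15/15 whatever the variance ratio. Only the degrees of freedom differ. Taking the background figures as variances gives a ratio of 0.71/0.31 = 2.29. If they are SDs, the ratio is 2.29² = 5.25. Over these two ratios, simulated pooled size is 5.1% to 5.4% at 20/20 and 15/15.

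Now suppose all 5 losses fall in the SCI group (15 v 20) and the variance ratio is 2.29:

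- Pooled SE = √{[(14 × 2.29 + 19 × 1)/33] × (1/15 + 1/20)} = 0.425.
- Correct SE = √(2.29/15 + 1/20) = 0.450.
- Ratio = 0.944.

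At a variance ratio of 5.25 the SE ratio is 0.904. Pooled size with no pair correlation is 6.4% and 7.9% respectively; Welch stays at about 5.0%. If the losses fall among the controls instead (20 v 15), pooled size drops to 4.0% and 3.4%.

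**4. Both effects together.** They pull in opposite directions. Pooled size at 15 SCI v 20 controls is:

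| r | Variance ratio 2.29 | Variance ratio 5.25 |
|---|---|---|
| 0 | 6.4% | 7.9% |
| 0.1 | 5.5% | 7.2% |
| 0.3 | 3.9% | 5.6% |
| 0.5 | 2.2% | 4.2% |

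**The case against.** A reader might infer that unequal variances make the plan's standard errors wrong as they stand. The documents do not support that, for three reasons:

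- The plan never says pooled, and Welch is itself an unpaired t-test.
- The group sizes it states, 20/20 and 15/15, are equal, and there the two standard errors coincide.
- The background figures are free-living Tcore in 9 v 8 people. The trial uses a fixed chamber, a baseline ceiling on Tcore and a stop at a 0.5°C rise. Even the direction of any variance difference under heat is unknown, and nothing is reported by group for cognition, sweating, perfusion or blood pressure.

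This stands, and it reduces the variance question to a safeguard. Unequal numbers are still possible. The protocol times the heat cognitive battery in tetraplegia by the 0.5°C rise, and the primary aim expects 80% of SCI subjects to reach it. If that trigger applied to the whole SCI group, about 4 of 20 would have no stated time for the battery.

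On the matching, the opposing case is that ignoring a positive correlation is conservative, so no false-positive problem arises, and that the gain is trivial at d of about 1.26. Both are correct. However, the stated power names no endpoint and rests on preliminary data in 8 subjects, so it does not show that every secondary variable has so large an effect.

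Two further objections stand. The t-tests follow a MANOVA that also ignores the matching, so changing only the t-tests would not recover all the precision, and the sizes and powers above leave out that gate. Baseline adjustment between non-randomised groups changes the question being asked if the groups differ at baseline.

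**Conclusion.** The point holds as a loss of precision in the secondary comparisons. The design matches on age and gender, and the analysis does not use it.

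The size depends on a correlation that the documents do not give. The standard error is 5% to 41% too large over assumed r of 0.1 to 0.5. At an assumed d of 0.8, using the pairs costs about 2 points of power at r = 0, gains about 9 points at r = 0.3 and about 16 at r = 0.5. At the d implied by the stated power, the difference is under 1 point throughout. These figures assume equal SDs, 20 complete pairs and one-to-one matching.

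Naming the t-test variant is a safeguard only. A pooled test reaches about 6% to 8% size only if losses fall mainly in a more variable SCI group and pair correlation is near zero. The largest effects of the two limbs cannot occur together.

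A reader might also infer that the primary results are compromised. They are not, because those tests make no comparison with controls.

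**What to change.** - State whether matching is one-to-one or by frequency.
- In both the MANOVA and the follow-up comparisons, include age and gender as covariates; this works under either type of matching. If matching is one-to-one, the alternative is a mixed model with a random pair effect, which keeps subjects whose partner is lost.
- Where a simple two-sample test is kept, name it as Welch.
- Baseline adjustment across these non-randomised groups is not part of this fix.

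The cost is a change of wording in the analysis section, since age and gender are already needed for matching. Statistically, the covariates take 2 degrees of freedom (38 to 36 at 20/20). The pair approach costs about 2 points of power (69% to 67% at d = 0.8) if the pair correlation is zero. Welch changes nothing material at 20/20 or 15/15.
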